### d) Study Timelines

The recruitment and enrollment process will be active for approximately 24 months. The anticipated final date for this study is 7/2017. The patients will be informed of the length of the study, which will include 8 visits in total. There will be a screening visit, baseline visit when they will receive the study medication, a visit eight hours after the first dose of medication is taken (baseline) where blood pressure will be checked, 4 weeks of medication administration and weekly monitoring, and a visit eight hours after the dosage of the medication is increased (week 2) where blood pressure will be checked. They will be informed of all of the study procedures for each week, including assessments and medical tests.

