### f) Procedures Involved in the Human Research

All eligible subjects will undergo visits at screening, baseline (week 0), visit 8 hours after week 0, week 1, week 2, visit 8 hours after week 2, week 3, and week 4 (end of study). The parameters of study drug dosing are as follows: isradipine as utilized in this trial will be administered twice daily. Isradipine will be titrated as follows: baseline (week 0) 5 mg/day BID; Week 2 increase to 10 mg/day BID if 5 mg was well-tolerated. Dosing will be flexible based on side effects with a maximum=10 mg/day. If 5 mg cannot be tolerated, the subject will be discontinued. Dosing was based on package labeling for hypertension and prior studies in Parkinson's disease (Simuni et al. 2010).

	Protocol Title:	A Molecular Approach to Treat Cognition in Schizophrenia: Ca 2+ Channel Blockade
	Principal Investigator Name/Contact Info:	[name] [contact]
	Primary Contact Name/Contact Info:	[name] [REDACTED]
	Date Revised:	May 16, 2017
	Study Number:	HSM# 12-0031, GCO# 12-0679, GCO# 13-1987

Measures described in detail below:

Safety Outcome Measures

- The Side Effects Checklist (SEC; physician administered) and side effect self-report form – (all visits)
- Vital signs including blood pressure (standing/supine – all visits)
- Blood pressure check within 8 hours of first dose. Staff contact number will be given to subject in case there are any problems before the 8 hour BP check (week 0). An additional blood pressure check 8 hours after increased dosage (week 2).
- Electrocardiogram (ECG); chemistry panel and CBC via blood draw (approximately 2 TSP blood drawn); urinalysis (screening & week 4)
- Urine toxicology (screening)
- Urine pregnancy test for women of childbearing potential (baseline)
- Abnormal Involuntary Movement Scale (AIMS) and Simpson Angus Scale (SAS) (all visits)
- Beck Scale for Suicidal Ideation (SSI) and Columbia Suicide Severity Rating Scale (C-SSRS) (all visits)

Clinical/Symptom Measures

- Structured Clinical Interview for the DSM-IV (SCID-IV) (screening)
- Symptom rating scales including the Brief Psychiatric Rating Scale (BPRS), the Scale for the Assessment of Negative Symptoms (SANS), the Hamilton Rating Scale for Depression (HRSD), the Clinical Global Impression Scale (CGI), the Clinician Administered Rating Scale for Mania (CARS-M) (all visits)

Neurocognitive/Functional Measures

- MATRICS Consensus Cognitive Battery\* (baseline & week 4)

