Data from this study may be used in medical publications or presentations. The information will be de-identified so that individual subjects cannot be recognized and the information will no longer be considered PHI. The information that is collected for research will be analyzed for many years and it is not possible to know how long this analysis and follow-up will take. Therefore, participants are allowing access to this information indefinitely.

Subjects will only be identified with a numerical code in compliance with HIPAA regulations. Raw subject data will be secured in double locked physical control. Digitized raw data will be similarly de-identified using coding and will be secured on an MS SQL server with Windows integrated security.

	Protocol Title:	A Molecular Approach to Treat Cognition in Schizophrenia: Ca 2+ Channel Blockade
	Principal Investigator Name/Contact Info:	[name] [contact]
	Primary Contact Name/Contact Info	[name] [REDACTED]
	Date Revised:	May 16, 2017
	Study Number:	HSM# 12-0031, GCO# 12-0679, GCO# 13-1987

Data analysis plan is included below. All analyses will be based on an intent-to-treat sample of subjects who received at least one dose of isradipine. Since the missing values may be dependent on the observed outcomes, we assume the missing data mechanism to be missing at random, and hence a mixed models analysis will be used to assess the treatment effect of isradipine with fixed effects for week and first order autoregressive covariance structure to evaluate change over time for all of the primary outcome measures. Cognitive measures will be handled differently, as these will only be collected at two time points – if missing data are substantial (or a complete visit is missing), subjects' data will not/cannot be meaningfully analyzed.

*Primary Analyses* will test the following hypotheses based on our specific aims:

To determine the feasibility of 4 weeks of isradipine on cognitive outcomes in SZ.  
Hypothesis: We will successfully recruit up to 80 stable schizophrenia and schizoaffective patients

To determine the safety of 4 weeks of isradipine on cognitive outcomes in SZ.  
Hypothesis: The frequency of new or worsened side effects (clinician-rated; self-reported; lab-based) will not be significantly different from baseline to end of study visit.

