A Fisher exact test will compare time-points by frequencies of new or worsened (compared with baseline) side effect severity ratings – this will be done for all side effects assessed by the SEC.

Differences on laboratory measures (chemistry panel, etc.) will be tested using repeated measures ANCOVA (baseline and week 4) and changes in vital signs (specifically blood pressure) will be assessed using mixed model ANCOVA, to incorporate data at each weekly visit.

Differences on SAS and AIMS total scores will be examined by calculating the  $\tau$ -b rank correlation between score and week for each subject and comparing the distribution of these trend scores with the Conover-Salsburg rank test.

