### **i) Provisions to Monitor the Data to Ensure the Safety of subjects**

Safety monitoring will be done on a patient by patient basis by the PI and the study physician on weekly visits. Side effects will be monitored closely and all AEs recorded. To increase safety, a blood pressure check will be done within 8 hours of this first dose (baseline). Staff contact number will be given to subject before the first dose in case there are any problems before the 8 hour BP check. Additionally, a blood pressure check will be done within 8 hours of increasing the dosage (week 2).

	Protocol Title:	A Molecular Approach to Treat Cognition in Schizophrenia: Ca 2+ Channel Blockade
	Principal Investigator Name/Contact Info:	[name] [contact]
	Primary Contact Name/Contact Info:	[name] [REDACTED]
	Date Revised:	May 16, 2017
	Study Number:	HSM# 12-0031, GCO# 12-0679, GCO# 13-1987

The PI will summarize all safety related outcomes after each set of 5 patients have completed the study and discuss these results with study physicians. This monitoring will be applied sooner than 5 patients if indicated, or if a SAE or unanticipated event occurs. All SAEs will be reported to the IRB within 24 hours and documented as per protocol. In the case that there are safety concerns from the PI or the IRB, this will be addressed in an ongoing manner. Independent of any SAEs, a Data Safety Monitoring Plan will be submitted to the IRB after the first 15 participants have been enrolled.

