Along with closely monitoring for symptom exacerbation, each visit with the study physician will entail a detailed side effect evaluation, which will include vital signs and a side effect checklist. The most common side effects of isradipine include hypotension, edema, headache, dizziness, palpitations, fatigue, flushing, and constipation. Patients will be educated about the potential for hypotension and its symptoms, and blood pressure and symptoms will be measured at every visit. If the patient develops clinically significant hypotension (e.g., systolic blood pressure equal to or less than 90 mm Hg or diastolic equal to or less than 60 mm Hg, or if they experience significant associated symptoms), or if at any point in the study subsequent to baseline there is a blood pressure drop of 20% or more from blood pressure at baseline, they will be discontinued from the study medication and excluded from the protocol. Rare side effects have also been reported including arrhythmias, syncope, severe hypotension or myocardial infarction. The informed consent process will alert subjects to these potential risks and close monitoring will ensure prompt response to any adverse effects with appropriate treatment and/or study discontinuation, as indicated.

Additional risks are minimal and involve the completion of questionnaires, interviews and paper-pencil/computerized tests. Some of the questions may be distressing to the individual and subjects will be told that they may refuse to answer any questions that they so choose. The testing procedure can sometimes cause fatigue but we will ensure plenty of resting periods during the session and will instruct subjects to notify staff if they would like an additional break. Pain and bruising may be associated with the blood draw for screening labs; however, a trained phlebotomist will perform the procedure to avoid any additional discomfort.

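### The blood-pressure model is described as using weekly data and does not say how the two 8-hour readings enter, though either can remove a patient; if they are left out, the on-drug fall is likely to be understated

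*Combined protocol and SAP*

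**What the plan says.** The analysis plan in section 5h gives one sentence to the blood-pressure model: "changes in vital signs (specifically blood pressure) will be assessed using mixed model ANCOVA, to incorporate data at each weekly visit". The same sentence analyses laboratory values at two time points only.

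Section 5f lists the visits after screening and baseline as "visit 8 hours after week 0, week 1, week 2, visit 8 hours after week 2, week 3, and week 4". Section 5d describes "a visit eight hours after the first dose of medication is taken (baseline) where blood pressure will be checked", and a matching visit after the week 2 increase. Section 5f also requires blood pressure at every visit.

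Section 6 gives the removal criteria. The absolute limits, offered as examples, are "systolic blood pressure equal to or less than 90 mm Hg or diastolic equal to or less than 60 mm Hg". Significant associated symptoms also count. The relative criterion applies at any point after baseline: if there is a "drop of 20% or more from blood pressure at baseline, they will be discontinued from the study medication and excluded from the protocol".

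Section 5h bases all analyses on an "intent-to-treat sample of subjects who received at least one dose of isradipine". For missing values it says "we assume the missing data mechanism to be missing at random", on the ground that missingness may depend on outcomes that were observed.

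Section 5j provides for safety measures at termination, without saying whether they enter any model.

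**The concern.** Either 8-hour reading can end a patient's participation. If the model takes the weekly visits alone, two kinds of patient lose the informative value:

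- A patient removed at the first 8-hour check has had a dose and so belongs to the analysis set, but gives the model only a pre-dose value.
- A patient removed at the second check gives no modelled reading after the dose increase.

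In both cases missingness depends on a value that the model never sees. The plan's reason for assuming missing at random, dependence on observed outcomes, does not cover that. The patients lost tend to be those with the largest falls or the lowest pressures, so the on-drug fall estimated from the rest leans low.

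Section 6 names hypotension first among the common side effects, the 8-hour checks exist to catch it, and this model is the only analysis named for the size of the fall.

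**Working it through.** **1. Are the 8-hour checks separate visits?** Section 5d states 8 visits. The list in section 5f gives 1 screening + 5 weekly (weeks 0, 1, 2, 3, 4) + 2 eight-hour = 8. The total reproduces only if the two checks are visits in their own right.

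**2. Could the labels settle it?** The first check is tagged as baseline in sections 5d and 5i and as week 0 in the measures list of section 5f; the second is tagged as week 2 in all three. Filing them under those weeks does not help. A post-dose value filed under week 0 contaminates the baseline and also shrinks the fall.

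**3. Direction and size.** The plan has no blood-pressure figure to reproduce, so every input here is assumed. The section 6 limits and the 20% criterion were applied in visit order to simulated systolic and diastolic readings. A likelihood-based repeated-measures model with unstructured covariance was then fitted to systolic pressure, (a) on the five weekly readings and (b) on all seven. Shortfall = true on-drug fall − estimated fall.

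First set: 11 scenarios of 40,000 patients, with baseline systolic 122 (SD 11), diastolic about 78, and visit noise 6/4 mmHg. Five of them, as mean fall over weeks 1 to 4 in mmHg:

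| Assumed case (fall before/after increase; SD of response) | Removed at an 8-hour check | True | Weekly only | Shortfall | All readings | Shortfall |
|---|---|---|---|---|---|---|
| 3/6; SD 0 | 7.1% | 4.580 | 4.421 | 0.159 | 4.545 | 0.035 |
| 3/6; SD 8 | 13.1% | 4.584 | 3.275 | 1.309 | 4.349 | 0.235 |
| 5/10; SD 8 | 20.0% | 7.583 | 5.846 | 1.737 | 7.267 | 0.316 |
| 5/10; SD 8; 8-hour fall 1.5 times weekly, correlation 1 | 34.1% | 7.594 | 5.180 | 2.414 | 7.176 | 0.418 |
| As above, correlation 0 | 34.5% | 7.592 | 6.915 | 0.677 | 7.526 | 0.066 |

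Correlation here is between a patient's 8-hour and weekly responses; in the first three rows it is 1 and the mean 8-hour fall equals the weekly fall. In all 11 scenarios the weekly-only fall was too small, by 0.2 to 2.4. With all readings the shortfall was 0.04 to 0.4.

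Second set: 216 scenarios of 60,000 patients. Inputs: systolic 120 (between-person SD 12), diastolic 78 (SD 8), within-person SD 7/5.25 or 5/4, week-4 fall 3, 6 or 9 mmHg, response SD 0.5 or 1 times the mean, 8-hour fall 1 or 1.5 times the sustained fall, correlation 0, 0.5 or 1, diastolic trigger off or on. One third of the scenarios let only half of triggering readings lead to removal. Removal at an 8-hour check ran from 1.5% to 38.8%. Week-4 results with unstructured covariance:

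- Weekly only: too small in 216 of 216; shortfall 0.06 to 4.44, median 0.41.
- All readings: bias −0.36 to +0.07 (negative means understated).
- Week-4 fall set at 6, 8-hour ratio 1, correlation 0.5, response SD 0.5: shortfall 0.13 to 0.63 across the two within-person SDs and with or without the diastolic trigger. With response SD 1, within-person SD 7 and the diastolic trigger on, 6.23 − 5.29 = 0.94, and with all readings 6.23 − 6.09 = 0.14.

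**4. Control.** In 72 scenarios where only weekly readings triggered removal, the unstructured weekly-only bias was at most 0.06 with systolic triggers and 0.32 with diastolic triggers added. So with systolic triggers the bias comes from leaving out the 8-hour readings. A smaller part comes from diastolic triggers, which a systolic model cannot see at any visit.

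**5. Other target.** If removed patients count as back at baseline, the weekly-only estimate is too large in 215 of 216 scenarios.

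**The case against.** A reader might infer that the plan excludes the 8-hour readings. The text does not go that far. The word weekly may only contrast with the two-point laboratory analysis in the same sentence, and blood pressure is required at every visit. What stands is that the plan does not say how these readings enter.

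A reader might also infer that the plan will understate the fall. That needs at least one removal at an 8-hour check, and it needs an on-drug target, which section 5h does not state; its intent-to-treat wording could point elsewhere. For an average over all on-drug readings the direction is not fixed either. With an 8-hour fall half the weekly one, the weekly-only result matched that average (6.3 against 6.3) or exceeded it (7.1 against 6.3).

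Larger shortfalls appear under first-order autoregressive (AR(1)) covariance (median 0.79, up to 5.47), but they mix in a separate issue. In the control scenarios AR(1) alone gave bias up to 0.73, or 1.32 with diastolic triggers. Section 5h ties AR(1) to the primary outcome measures and names no covariance for blood pressure, so those figures should not lead.

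The simulations model a single systolic outcome. The plan says only blood pressure, and section 5f calls for standing and supine readings.

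Finally, the stated safety hypothesis concerns the frequency of side effects. The Fisher exact test in section 5h, the adverse-event records and the safety summary after every five completers in section 5i still capture removed patients. This limits the consequence but does not remove the gap.

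**Conclusion.** The point holds in conditional form. The plan does not say how two scheduled readings that can remove a patient enter the blood-pressure model. If they are left out and anyone is removed on one of them, missing at random fails for that patient, and the modelled on-drug weekly fall is likely to be too small.

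The size cannot be fixed from the documents. Under the assumed inputs it is often a few tenths of a mmHg and exceeds 2 mmHg only in the more extreme cases. The conclusion rests on an on-drug target, on a likelihood-based model, and on patients being removed at the 8-hour checks. It would be wrong to infer that the trial's safety assessment as a whole is compromised: the harm is confined to the blood-pressure estimate.

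**What to change.** In section 5h:

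- State that the target is the on-drug change in blood pressure.
- Enter both 8-hour readings, including any reading that led to removal, as their own categorical time points, separate from baseline and week 2.
- Say how termination readings under section 5j are handled, and keep off-drug values out of the on-drug target.
- Report the number removed for blood pressure by visit and by trigger (systolic, diastolic, symptoms).
- Check sensitivity to the covariance structure, for example unstructured against AR(1), rather than rely on one. This matters because adding the readings under AR(1) recovered a median of only 29% of the bias.

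The timing must also be reconciled. Section 5d places both checks eight hours after dosing. Section 5i puts them inside an 8-hour window (for the increase, "a blood pressure check will be done within 8 hours of increasing the dosage (week 2"). Section 5f uses both forms. A categorical 8-hour time point needs one definition.

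The cost is wording, since the readings are already collected, plus some model parameters. Unstructured covariance over seven readings has 7 × 8 / 2 = 28 parameters, against 5 × 6 / 2 = 15 for the five weekly readings. The gain depends on enrolment, which is only capped at 80. In one case towards the high end of the grid (15.9% removed at an 8-hour check), weekly-only AR(1) was compared with all-readings unstructured, so both features changed. Root mean squared error was 2.25 against 1.59 at n = 80, but 3.12 against 3.05 at n = 25, where the SD of the estimate rose from 2.78 to 3.05. Near 25 patients there is little net gain in precision.

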### 1) Objectives:

In this project we propose to conduct a 4-week open label cognitive enhancement trial of isradipine in up to 80 stable outpatients with schizophrenia and schizoaffective disorder.

The primary aim of this study is to evaluate the effects of the calcium channel antagonist, isradipine on cognitive dysfunction in patients with schizophrenia and schizoaffective disorder. Incomplete treatment response is common. Cognitive impairment and negative symptoms persist in a majority of patients even when positive psychotic symptoms are well-controlled, and they account for a large proportion of the variance in explaining functional disability (Keefe et al. 2007). This has led to a focused effort to target the specific treatment of cognition in patients with schizophrenia (Green and Nuechterlein, 2004), with somewhat limited success to date.

Novel treatment options have been limited by an incomplete understanding of the biological etiology of schizophrenia; however, recent data from the field of genomics have provided insights into the molecular underpinnings of schizophrenia and its associated symptoms. The majority of genetic risk loci identified to date show trans-disorder effects, increasing susceptibility across a broad range of neuropsychiatric disorders including schizophrenia and bipolar disorder (Williams et al. 2011; Purcell 2009). One possible explanation for this overlap is that several of these genes are influencing risk via their effects on shared phenotypes such as neurocognitive dysfunction. One such example is a single nucleotide polymorphism (SNP; rs1006737) in the calcium channel gene, CACNA1C; initially associated with bipolar illness (Sklar et al. 2008; 2011; Ferreira et al 2008) but also linked with schizophrenia (Green et al. 2009; Nyegaard et al. 2010) and recurrent major depression (Green et al, 2009). The strength of

	Protocol Title:	A Molecular Approach to Treat Cognition in Schizophrenia: Ca 2+ Channel Blockade
	Principal Investigator Name/Contact Info:	[name] [contact]
	Primary Contact Name/Contact Info:	[name] [REDACTED]
	Date Revised:	May 16, 2017
	Study Number:	HSM# 12-0031, GCO# 12-0679, GCO# 13-1987

the association signal for CACNA1C in major mental illness is unambiguous and several subsequent studies have evaluated the effects of CACNA1C variation on neurocognitive capacity.

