### b) Inclusion and Exclusion Criteria

**Inclusion criteria:** **1.** Age 18-60; **2.** DSM-IV schizophrenia or schizoaffective diagnosis; **3.** Residual phase of illness criteria met at screen and baseline as defined by item scores of  $\leq 4$  on each of the Brief Psychiatric Rating Scale (BPRS) hallucinatory behavior, unusual thought content, and conceptual disorganization items; **4.** Hamilton Rating Scale for Depression (HRSD)  $\leq 12$ ; **5.** Baseline Clinician Administered Ratings Scale for Mania (CARS-M) score of  $< 5$ ; **6.** Simpson Angus Scale (SAS) total score of  $\leq 6$ ; **7.** Treatment with at least one but no more than two stably-dosed second-generation antipsychotic medication (other than clozapine) for  $\geq 2$  months and no changes planned over the 4-week study period. First generation antipsychotics and clozapine are thought to cause significant cognitive impairment. Initial baseline cognitive functioning will not be evaluated as inclusion/exclusion criterion because schizophrenia/schizoaffective disorder have a relatively cognitively homogeneous patient sample. We do not anticipate any subjects without cognitive impairment. We will cover for baseline performance to determine if degree of cognitive impairment at baseline is responsible for any change noted.

**Exclusion criteria:** **1.** History of CNS trauma, neurological disorder, ADHD, mental retardation, learning disability, or other non-schizophrenic cause of cognitive impairment; **2.** DSM-IV diagnosis of substance abuse/dependence within 3 months or positive urine toxicology at screening that is not consistent with what participant reported. Substance abuse and dependence are determined based on an extremely comprehensive interview (the SCID), which evaluates lifetime history and current history of all substance use disorders. As per the protocol, DSM-IV diagnosis of substance abuse or dependence within 3 months will be exclusionary (not substance use); **3.** Pregnant women or women of child bearing potential who are not using a medically accepted means of contraception (including oral contraceptive or implant, condom, diaphragm, spermicide, intrauterine device, tubal ligation, or partner with vasectomy) **4.** Women who are breastfeeding; **5.** Active, unstable medical problem that may interfere with cognition; **6.** Current treatment for hypertension; **7.** Uncontrolled hypertension; **8.** History of heart

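### The only planned analysis of SAS and AIMS is a per-subject tau-b against week, which ignores the size of a rise, is undefined for unchanged scores and can score an early, settling rise as no change or improvement

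*Combined protocol and SAP*

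**What the plan says.** The safety part of the primary analyses, in section 5(h), reads "Differences on SAS and AIMS total scores will be examined by calculating the" tau-b "rank correlation between score and week for each subject and comparing the distribution of these trend scores" "with the Conover-Salsburg rank test". No other analysis of these two scales is stated. The Fisher comparison of new or worsened ratings against baseline covers the Side Effects Checklist ("this will be done for all side effects assessed by the SEC"), not SAS or AIMS. The mixed model is stated for the primary outcome measures, while SAS and AIMS are given the tau-b method.

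Section 5(f) lists "Abnormal Involuntary Movement Scale (AIMS) and Simpson Angus Scale (SAS) (all visits". After screening, the visits are "baseline (week 0), visit 8 hours after week 0, week 1, week 2, visit 8 hours after week 2, week 3, and week 4". The plan does not say which of these enter the tau-b.

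Inclusion criterion 6 in section 5(b) requires a "Simpson Angus Scale (SAS) total score of" 6 or less. Section 5(h) bases all analyses on everyone who took at least one dose. It has no rule for a subject whose scores are all tied.

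**The concern.** The issue is the number computed for each subject, whatever test is applied to it afterwards. A safety summary for a movement scale should show who got worse than at baseline, and by how much. Tau-b against week answers a different question: whether the score tends to move in one direction over the weeks.

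Three consequences follow.

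- A trivial rise and a severe rise can get the same value.
- A subject with no change has no value at all. Under an entry cap of 6 on SAS, flat low scores are plausible.
- A subject who worsens early and then recovers can contribute a negative value, which offsets harm in other subjects.

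Nothing else in the stated analysis of these scales would bring such harm to light.

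**Working it through.** The documents give no sample-size, power or alpha figure for this analysis, so there is no figure of the plan's to reproduce. All score profiles below are illustrative assumptions, because the documents contain no SAS or AIMS data.

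**Formula.** tau-b = (C - D) / sqrt((n0 - n1)(n0 - n2)). C and D are the concordant and discordant pairs, n0 is all pairs, and n1 and n2 are the pairs tied on week and on score. For weeks 0 to 4, n0 = 10 and n1 = 0.

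**Size of the rise.** For 0,0,0,0,1: C = 4, D = 0, n2 = 6, so 4 / sqrt(10 × 4) = 0.632. For 0,0,0,0,15 the counts are the same, so the value is again 0.632. With only two readings, 0 to 1 and 0 to 12 both give 1/1 = +1.

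**No change.** For 0,0,0,0,0: C = D = 0 and n2 = 10, so 0 / sqrt(10 × 0) is undefined. The same holds for 3,3,3,3,3.

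**Early rise that settles.** For 0,8,6,3,0: C = 3, D = 6, n2 = 1, so -3 / sqrt(10 × 9) = -0.316. For 2,8,6,4,3, where week 4 is still above baseline: C = 4, D = 6, so -2/10 = -0.200. All profiles were then listed that start at 0, peak at week 1 (peak 1 to 6), do not rise again and are back at 0 by week 4. Of these 83, 77 are negative, 6 are zero (peak held through week 3) and none is positive.

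**Limits of the reversal.**

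| Profile | Visits | tau-b |
|---|---|---|
| 2,2,8,2,2 (peak at week 2) | weeks 0-4 | 0 |
| 2,2,2,8,2 (peak at week 3) | weeks 0-4 | +0.316 |
| 2,8,5,5,5 (partial settling) | weeks 0-4 | +0.120 |
| 2,2,8,2,2,2 (peak at week 1) | screening + weeks 0-4 | -0.115 |
| 2,2,8,6,4,2 (peak at week 1) | screening + weeks 0-4 | 0 |

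With screening added, the 83 profiles split into 21 negative, 26 zero and 36 positive.

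**Simulation.** The assumptions are 80 subjects, weeks 0 to 4, 40-60% with scores of 0 unless affected, the rest Poisson with mean 1.5, and 15% affected. A one-sided 5% one-sample t-test is applied to each summary. It stands in for the planned rank test so that the two summaries are compared on equal terms; with no effect, each rejects in about 5% of trials.

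| Assumed harm | tau-b detects | Mean on-treatment change detects |
|---|---|---|
| Rise of 6,5,2,0 at weeks 1-4, all stay on drug | about 1% or fewer | about 87-93% |
| Same rise, subject withdrawn after a rise of 5 or more | about 83-91% | not needed for the point |
| Rise of 0,2,6,6 (after the week 2 dose step) | 83-92% | 90-96% |
| Rise of 1 point at weeks 3-4 | 52-77% | 17-21% |

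In the first row, 97-98% of affected subjects with a defined tau-b score zero or below.

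**The case against.** The strongest reply is that the early-harm scenario keeps visibly worsened subjects on drug. Section 5(j) discontinues subjects with clinical worsening noted by the study physician, and section 6 does so for clear symptom worsening. A subject with scores 0,8 who then leaves has tau-b +1, the most adverse value, and detection recovers to about 83-91%. This stands as a limit, but the threshold of 5 points is an assumption: section 5(j) names no SAS or AIMS score. Where the physician does not judge the rise to be worsening, the low detection remains.

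The scenario is also close to the worst case for tau-b. For harm that follows the week 2 dose step the gap is modest, and for small late rises tau-b is the more sensitive summary. Ignoring size is a known property of rank methods for ordinal scales, so full replacement is partly a trade-off. That is fair.

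A reader might infer that unchanged subjects drop out of the analysis. The plan does not say so; it is silent, and scoring them 0 would repair that one gap. It would leave the early-harm result essentially unchanged, at about 0.1% detection. A reader might also take the simulated share of undefined values, 34-60%, as a forecast. It mostly restates the assumed 40-60% of subjects at zero.

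Finally, there are other safeguards: the checklist analysis, weekly physician review, and a safety summary after every 5 completers. The side effects listed in section 6 include no movement disorder, and the safety hypothesis does not name SAS or AIMS. These points lower the stakes, but none of them is an analysis of SAS or AIMS scores.

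**Conclusion.** The point holds in a limited form. Two defects are exact whichever visits are used: tau-b ignores the size of a rise, and it is undefined for a constant score, for which the plan has no rule. The third is conditional. On weeks 0 to 4, a week 1 rise that has returned to baseline by week 4 is scored as zero or negative.

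The documents do not support the broader reading that tau-b generally records harm as improvement, or that the analysis has almost no chance of finding early movement effects. Both depend on the timing of the peak, the visits included, and affected subjects staying on drug. The simulated percentages rest on assumed score distributions and a stand-in test. They show direction and rough size only.

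This should be fixed. It does not invalidate the trial's safety assessment.

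**What to change.** In section 5(h), make the main summary for SAS and AIMS each subject's mean on-treatment score minus baseline, using all post-baseline readings, including any termination visit. Report the mean with a bootstrap 95% confidence interval over all dosed subjects with at least one on-treatment reading. Add the number with any rise above baseline and the worst on-treatment score. Keep unchanged subjects in the denominator.

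If tau-b is kept as a supplementary trend measure, score constant series as 0 and state which visits enter.

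The cost is a change of wording and a little more analysis, with no new data. A mean change is more affected by one extreme score and less sensitive to small late rises. The count of subjects with any rise and the worst score make the first visible; keeping tau-b as a supplement covers the second.
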